4.4. Sub-Group Analyses

Subgroup analyses will be carried out to assess whether the effect of treatment varies across subgroups defined according to the following criteria:

- Patients enrolled vs. not enrolled/treated in other therapeutic clinical trials
- ≥ 60 years versus less than 60 years of age
- Sex
- Ethnicity
 - White/Black/Hispanic/Asian/Other

- Presence of medical co-morbidities
 - diabetes (yes/no)
 - cardiac (yes/no)
 - respiratory (yes/no)
- Smoking History
 - Ever smoker/current smoker/never
 - 15 pack year history of smoking versus not
- Obesity (BMI ≥ 30 vs <30)
- Onset of symptoms > 12 days before randomization (including non-respiratory symptoms) versus not
- Timing of administration of CCP from diagnosis of COVID-19 (≤ 72 hours vs >72 hours)
- Severity of illness of donors (hospitalized vs not)
- ABO blood type of recipients (A vs other, B vs other, O vs other, AB vs other)
- Detectable vs non-detectable viral plasma viral load at baseline
- Anti-SARS-CoV-2 seropositivity at baseline
- Oxygen status at baseline ($\leq 2L$ vs $> 2L$)

These subgroup analyses will be carried out by estimating the treatment effect within subgroups and providing 95% confidence intervals and p-values.

In addition the effect of plasma from one donor will be compared to the effect of plasma from two donors.

Any additional exploratory sub-group analyses carried out will be based on regression models involving treatment, the subgroup variable and the respective interaction. The findings from such post-hoc analyses will be reported as hypothesis generating if the test of the null hypothesis that the interaction term is zero gives a statistically significant finding of heterogeneity of the effect.

4.5.Safety Reports for the IDSMC

Monthly reports on logistical issues, donor recruitment, and patient accrual overall and by study site will be provided to the IDSMC. Information on antibody test results will also be provided as available. These reports will also give tabulations of i. adverse events, ii. serious adverse events, and iii. CPP transfusion-related adverse events. If the IDSMC requests more or less frequent reports on this data, they will be provided. The reports will be created by an independent statistician who is unblinded to the treatment assignment.

4.6.Exploratory Analysis of the Role of anti-SARS-CoV-2 antibodies

4.6.1.Neutralizing antibodies

Donor samples will be tested for the presence of total anti-SARS-CoV-2 antibodies and neutralizing antibodies for all CCP units transfused. Moreover, there will be samples taken from

study participants to assess antibody titre at the time of randomization and 48 hours later. The results of the donor antibody testing will be used to study the effect of neutralizing antibodies on clinical outcomes. The results of antibody testing of participants will enable investigation of the effect of CCP transfusion on participant antibody levels.

The total and neutralizing antibody titres for the donor samples will be recorded. In order to assess the effect-modifying role of these titres on the outcome, we will consider regression models for the primary outcome with covariates based on treatment arm, titres and interactions terms. For the primary binary outcome, a logistic regression model will be fitted involving the treatment indicator (equaling 1 for those in the CCP arm), an "interaction term" defined as the product of the treatment indicator and the log transformed and centered total antibody titre for the plasma transfused, and a second "interaction term" defined as the product of the treatment indicator and the log transformed and centered neutralizing antibody titre for the plasma transfused. The main effect of treatment will then correspond to the effect of CCP for a unit with the geometric mean total antibody titre and the geometric mean neutralizing antibody titre. The coefficient of the first "interaction term" will reflect how this CCP effect is moderated according to the total antibody titre for the plasma sample transfused, while the second "interaction term" will reflect how the CCP effect is moderated by the neutralizing antibody titre of the plasma sample transfused; the phrase "interaction term" is in quotation marks because the main effects for these titre based variables are not included in the linear predictor.

Similar analyses to those for the total and neutralizing antibodies will be carried out incorporating information of the patients own total and neutralizing antibody profiles prior to the plasma transfusion to explore how the benefit of CCP may vary depending on the antibody profile of the recipient. These analyses will be carried out at the interim analysis for the IDSMC and at the time of study completion.

For a fuller description of the handling of the laboratory data and analyses please see *Statistical Analysis Plan for A Randomized Open-Label Trial of CONvalescent Plasma for Hospitalized Adults with Acute COVID-19 Respiratory Illness: Supplement Regarding Antibody Analyses*

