12. STATISTICAL CONSIDERATIONS

12.1. Sample Size Considerations

Assuming a baseline risk of intubation or death by Day 30 of 30% in hospitalized patients with standard of care, a sample size of 1200 (800 in the CCP arm, and 400 in the standard of care arm) would provide 80% power to detect a relative risk reduction of 25% with CCP therapy using a 2-tailed test at level α = 0.05. This assumes no patient is lost to follow-up. Lost follow-up is expected to be minimal.

There is uncertainty about the intubation and mortality rate that will be observed in this study due to possibly evolving profile of COVID-19 patients admitted hospital over the course of the pandemic. To address this, a blinded sample-size re-estimation will take place when the primary outcome is available for 50% of the target sample. Sample size will only be adjusted if the estimated event rate is different than the originally specified event rate to a sufficient extent that the study is not expected to achieve the desired nominal power for the test of the primary outcome.

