12.4.4. Sub-Group Analysis

Subgroup analyses for the primary outcomes will evaluate the treatment effect across the following subgroups:

- Patients enrolled vs. not enrolled/treated in other therapeutic clinical trials
- >= 60 years versus less than 60 years of age
- Sex
- Ethnicity
 - White/Black/Hispanic/Asian/Other
- Presence of medical co-morbidities
 - diabetes (yes/no)
 - o cardiac (yes/no)
 - respiratory (yes/no)
- Smoking History
 - Ever smoker/current smoker/never
 - 15 pack year history of smoking versus not
- Obesity (BMI >= 30 vs <30)
- Onset of symptoms > 12 days before randomization (including non-respiratory symptoms)
 versus not
- Timing of administration of CCP from diagnosis of COVID-19 (<=72 hours vs >72 hours)
- Severity of illness of donors (hospitalized vs not)
- ABO blood type of recipients (A vs other, B vs other, O vs other, AB vs other)
- CCP from one donor vs CCP from two donors
- Detectable vs non-detectable viral plasma viral load at baseline
- Anti-SARS-CoV-2 seropositivity at baseline
- Oxygen status at baseline (≤ 2L vs > 2L)

A forest plot will display confidence intervals across subgroups. Interaction tests will be conducted to determine whether the effect of treatment varies by subgroup.

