1.3. Sample Size Justification

Assuming a 30% risk of the composite outcome of intubation or death by Day 30 among hospitalized patients under standard of care, a sample size of 1200 individuals (800 in the CCP arm, and 400 in the standard of care arm) will provide 80% power ($\beta = 0.20$) to detect a relative risk reduction of 25% with CCP therapy using a 2-tailed test at level $\alpha = 0.05$. We assume that no patient will be lost to follow-up.

2. Responses

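### SAP 4.4 omits the interaction tests that protocol 12.4.4 requires for the listed subgroups, and the within-subgroup p-values it names do not test whether the effect varies

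*SAP*

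**What the plan says.** Protocol 12.4.4 lists the subgroups for the primary outcome, asks for a forest plot of confidence intervals, and then commits to a test of heterogeneity: "Interaction tests will be conducted to determine whether the effect of treatment varies by subgroup". It does not mention p-values inside each level.

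SAP 4.4 gives its purpose as finding out whether the effect differs across subgroups. Its list is essentially the same; the one-donor v two-donor contrast moves from the list to a sentence of its own. For the listed subgroups the only method named is: "These subgroup analyses will be carried out by estimating the treatment effect within subgroups and providing 95% confidence intervals and p-values". A regression with treatment, subgroup and their interaction is described only for further exploratory subgroups, which the SAP calls post-hoc. The SAP neither repeats nor withdraws the protocol's sentence.

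**The concern.** Whether an effect varies is a question about the difference between two subgroup effects. A p-value inside each level answers another question: whether that level alone shows an effect. The answer depends heavily on how many patients the level contains. A factor can show p<0.05 in one level and not in the other because of size and chance, with an identical true effect in both.

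The list includes age, sex, ethnicity, comorbidity, baseline serostatus and oxygen need. If the within-level p-values are the only inferential result shown for these factors, readers are likely to compare them and draw conclusions about which patients benefit. The protocol already names the right test, and the SAP leaves it out for the planned subgroups while asking for it in the unplanned ones.

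**Working it through.** **Inputs.** Control risk: "Assuming a 30% risk of the composite outcome of intubation or death by Day 30" (SAP 1.3). Effect: "would provide 80% power to detect a relative risk reduction of 25% with CCP therapy" (protocol 12.1), so 0.30 × 0.75 = 0.225 and the difference is d = 0.075. Arms: "800 in the CCP arm, and 400 in the standard of care arm" (SAP 1.3). Test: "using a 2-tailed test at level α = 0.05" (protocol 12.1). Loss to follow-up: none (SAP 1.3).

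**Assumed, because the documents do not give them.** The share f of patients in the larger level (50%, 67%, 80%); 2:1 allocation kept within each level; 30% control risk in both levels. With equal control risk, a uniform effect is uniform on both the difference and the ratio scale.

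**Step 1: reproduce the plan's power.**
- Average risk: (400 × 0.30 + 800 × 0.225)/1200 = 0.25.
- Null SE: √[0.25 × 0.75 × (1/400 + 1/800)] = 0.026517.
- Alternative SE: √[0.30 × 0.70/400 + 0.225 × 0.775/800] = 0.027257.
- Power: Φ[(0.075 − 1.96 × 0.026517)/0.027257] = Φ(0.845) = 80.1%, against the stated 80%.
- With the unpooled Wald test: Φ(0.075/0.027257 − 1.96) = Φ(2.752 − 1.96) = 78.6%. The steps below use this form.

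**Step 2: power inside a level with share f.** The SE becomes 0.027257/√f, so power is Φ(2.752√f − 1.96), plus a small opposite tail.

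**Step 3: chance that exactly one of two levels has p<0.05.** With powers a and b in independent levels this is a(1 − b) + b(1 − a). For 80/20: 0.692 × 0.766 + 0.234 × 0.308 = 0.530 + 0.072 = 0.602.

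**Step 4: interaction test.** z = (D₁ − D₂)/√(SE₁² + SE₂²). Its SE is 0.027257/√[f(1 − f)]. Power for a true interaction equal to d is Φ(0.075/SE − 1.96), plus a small opposite tail. For 50/50: SE = 0.0545 and Φ(1.376 − 1.96) = 28%.

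| Split | Power, larger level | Power, smaller level | Exactly one p<0.05 | Same, given overall p<0.05 | Interaction test rejects, uniform effect | Power for interaction of 0.075 |
|---|---|---|---|---|---|---|
| 50/50 | 49% | 49% | 50% | 58% | 5.1% | 28% |
| 67/33 | 62% | 35% | 53% | 63% | 5.1% | 25% |
| 80/20 | 69% | 23% | 60% | 72% | 5.3% | 20% |

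The rejection rates come from 200,000 binomial simulations, which also gave 50%, 54% and 61% for exactly one p<0.05. The figures conditional on a significant overall result come from 400,000 normal draws. In the same draws, only 7–10% of the trials with a discordant pair also had a significant interaction.

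**Step 5: no effect at all.** Exactly one p<0.05: 2 × 0.05 × 0.95 = 9.5% per factor, against 5% for the interaction test.

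**The case against.** Several stronger readings are tempting, and the documents do not support them.

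- *The SAP has replaced the protocol's rule.* No passage says that the SAP overrides the protocol on subgroups. Protocol 11.8 requires the protocol to be followed exactly and sends changes through amendment. Read together, the documents still call for interaction tests. The defect is an omission that leaves them inconsistent.
- *The SAP decides subgroup effects by within-level p-values.* SAP 4.4 says such p-values will be reported. It states no criterion for declaring a subgroup effect from them. False claims are a foreseeable misreading, not something the plan prescribes.
- *The SAP uses interactions only post hoc.* That is true of section 4.4 but not of the whole SAP. Section 4.6.1 and the antibody supplement pre-specify treatment-by-marker interactions, including the patient's own antibody profile, which covers baseline serostatus in another form.
- *A uniform effect is bound to look like effect modification.* Per factor it is roughly an even chance if the design effect is real, and about 10% if there is no effect.
- *Interaction tests would cut the number of false flags.* Under no effect, simulations with 16 independent two-level factors (number, independence and prevalences of 5–45% all assumed) gave at least one within-level p<0.05 in 57–59% of trials and at least one significant interaction in 58–59%. The gain is that the right question is tested, not that fewer tests are run.

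It can also be said that confidence intervals inside each level allow the same misreading, and that the protocol does not forbid within-level p-values. Both points are fair. They are reasons to state what a claim must rest on, whatever else is tabulated.

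Finally, an interaction term cannot be fitted for every listed factor. Timing of CCP administration, donor severity and number of donors have no value in the standard-of-care arm. This limits the remedy but leaves the baseline factors, which are most of the list.

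**Conclusion.** The point holds as an inconsistency between SAP 4.4 and protocol 12.4.4 with a real statistical consequence. Followed alone, SAP 4.4 does not test the question it sets. If the planned effect is uniform, about 50–60% of trials would show p<0.05 in exactly one of two levels of a given factor, against about 5% flagged by an interaction test. With no effect the comparison is about 10% against 5%.

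These sizes rest on assumed splits from 50/50 to 80/20, equal control risk in both levels, 2:1 allocation within levels and two-sided 0.05. They are per factor; the documents do not give what is needed for a reliable count over the whole list, where some contrasts, such as the four ABO comparisons, are not independent. The wording should be corrected, but the primary analysis does not depend on it.

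**What to change.** Amend SAP 4.4 as follows.

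1. For listed factors defined in both arms, any statement that the effect varies rests on a treatment-by-subgroup interaction test. Name the model and scale; relative risk would match SAP 4.2.
2. Report the interaction estimate, its 95% CI and p-value, and the number of interaction tests done.
3. Present within-level estimates and 95% CIs as description.
4. For factors that exist only in the CCP arm (timing of administration, donor severity, one v two donors), state a separate comparison, for example within the CCP arm and labelled non-randomised.

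The change is to wording only and needs no new data; item 1 carries over what protocol 12.4.4 already requires. The cost is that interaction tests are weak here: about 20–28% power for an interaction as large as the planned effect. A non-significant interaction should not be read as proof that the effect is uniform. The number of tests is not reduced.

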4.6.2. Viral load

A sample from study participants will be collected at the time of randomization (up to 48 hours before randomization) and 48 hours later (up to 5 days later) to measure RNA levels of SARS-CoV-2. This information will enable an analysis of the effect of CCP on viral load.

4.7. Schedule for Primary Interim Analysis

A single interim analysis is planned when information on intubation or death at Day 30 is available for 50% of the target sample (600 patients: 400 in the CCP arm and 200 in the arm receiving standard care). An O'Brien-Fleming stopping rule will be employed with a threshold for formal statistical significance at the interim analysis of 0.0054 and the final significance level of 0.0492. The Independent Data Safety Monitoring Committee (IDSMC) may recommend early

termination or modification of the protocol only when there is clear and substantial evidence of a treatment difference. More details about the interim analyses are described below as well as a separate guidance document for the IDSMC.

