4.9. Interim Analysis

A single interim analysis is planned when the primary outcome (intubation or mortality at Day 30) is available for 50% of the target sample. An O'Brien- Fleming stopping rule⁴⁴ will be used at that time, but treated as a guideline, so there is minimal impact on the threshold for statistical significance for the final significance test of the primary outcome.

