12.2.2. Efficacy Review

A single interim analysis is planned when information on the primary outcome (composite of intubation or death at Day 30) are available for 50% of the target sample. The Lan-DeMets spending function⁵⁴ analog of the O'Brien-Fleming boundaries⁴⁴ will be used to monitor the primary endpoint as a guide for the DSMB for an overall two-sided type-I error rate of 0.05. Conditional power will be presented as an additional guide to the DSMB. Conditional power allows

computation of the probability of obtaining a statistically significant result by the end of the trial given the data accumulated thus far, incorporating a hypothesized treatment effect (e.g., the treatment effect assumed for sample size determination) thereafter. If conditional power is less than 20% under the original trial assumptions, consideration could be given to stopping the trial. An unblinded independent statistician will prepare the reports for IDSMC to review when making their recommendations. An IDSMC charter will further describe procedures and membership. An additional document on statistical methods related to the interim analyses will be provided to the IDSMC prior to their first meeting.

An additional document on statistical issues related to monitoring will be provided to the IDSMC prior to interim analyses.

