4.8. The Lan-DeMets Error Spending Function

In case any additional interim analyses are requested by the IDSMC, the flexible Lan-DeMets (Lan and DeMets, 1983) type I error spending function analog of the O'Brien-Fleming boundaries will be used to monitor the primary endpoint as a guide for the IDSMC for an overall two-sided type I error rate of 0.05 based on a two-sided test. This is defined as follows. If we let n denote the sample size according to the calculation for the planned study and n_o denote the number of individuals at an interim analysis, then let $t = n_o/n$. This "O'Brien-Fleming" error spending function has the form

$$\alpha(t) = 2 - 2\Phi(Z_{\alpha/2}/\sqrt{t})$$

where $Z_{\alpha/2} = 1.96$ reflects the critical value corresponding to the analysis that would be done for an analogous trial with a fixed sample size and a two-sided test (Lans and DeMets, 1983). For the interim analysis planned when 50% of the sample will be available $t = 1/2$ and we obtain

$$\alpha(1/2) = 2(1 - \Phi(Z_{\alpha/2}/\sqrt{0.5})) = 0.005573$$

as the threshold for significance and stopping at the interim analysis. This constitutes a conservative stopping rule which we will adopt to preserve much of the type I error for the analysis at the conclusion of the study, to minimize the bias in estimates of the treatment effect from sequential trials, and to gear the trial towards one that will be large enough to answer the several important secondary questions we aim to address including the effect of neutralizing antibodies.

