4.10. Sample Size Re-Estimation

There is uncertainty about the intubation and mortality rate that will be observed in this study due to possibly evolving profile of COVID-19 patients admitted to hospital over the course of the pandemic. To address this, a blinded sample size re-estimation will take place when the primary outcome is available for 50% of the target sample, which coincides with the time of the interim analysis report. Sample size will be adjusted if the estimated event rate is different from that originally specified to the extent that the study is not expected to achieve the desired nominal power for the test of the primary outcome. Friede and Kieser (2004) give the following formula for total sample size re-estimation: We let $n = n_e + n_s$ denote the total sample size where n_e and n_s denote the number of individuals in the experimental (CCP) and standard of care arms respectively, and let θ denote the randomization ratio where $n_s = \theta n_e = 0.5n_e$. We let d be the absolute risk difference we wish to detect (which was specified in the original sample size calculation). Then if we observe a pooled composite event rate p , then

$$n = n_e + n_s = \left(2 + \theta + \frac{1}{\theta}\right) \frac{(Z_{\alpha/2} + Z_{\beta})^2}{\delta^2} p(1 - p),$$

gives the revised total sample size.

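### SAP 4.7 and 4.8 give two interim thresholds for the same 50% look (0.0054 and 0.005573), and with the final level of 0.0492 neither holds the overall two-sided 0.05

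*SAP*

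**What the plan says.** SAP 4.7: "A single interim analysis is planned when information on intubation or death at Day 30 is available for 50% of the target sample", that is 600 patients (400 CCP, 200 standard of care). It names an O'Brien-Fleming rule with a "threshold for formal statistical significance at the interim analysis of 0.0054 and the final significance level of 0.0492".

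SAP 4.8 opens by offering a Lan-DeMets spending function for any further looks the IDSMC may request. It then evaluates that function "For the interim analysis planned when 50% of the sample will be available", obtains 0.005573, and presents it "as the threshold for significance and stopping at the interim analysis". It gives no final level of its own.

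Protocol 12.2.2 assigns the same Lan-DeMets analog to the single planned look, "as a guide for the DSMB for an overall two-sided type-I error rate of 0.05". Protocol 4.9 treats the rule as a guideline, "so there is minimal impact on the threshold for statistical significance for the final significance test of the primary outcome".

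SAP 4.10 re-estimates the total sample size at that same look. It holds fixed "the absolute risk difference we wish to detect (which was specified in the original sample size calculation".

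**The concern.** There are two separate faults. The first needs no calculation: one planned look has two printed thresholds, and the plan does not say which governs. The second is that an interim threshold and a final level come as a pair. Once the first is fixed at a given information fraction, the second follows from the overall error rate. The printed final level of 0.0492 is higher than either interim value allows, so a trial run by these numbers would have an overall error above 0.05.

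In addition, 0.0492 is fixed in advance, although SAP 4.10 can raise the total sample size. That lowers the information fraction at which the look took place, and no rule adjusts the final level.

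At stake is the decision threshold for the primary outcome. A result close to the boundary would invite dispute about which number applied.

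**Working it through.** **Inputs.** One look at t = 600/1200 = 0.5; interim 0.0054 and final 0.0492 (SAP 4.7); interim 0.005573 (SAP 4.8); overall two-sided error 0.05 (SAP 4.8, Protocol 12.2.2). From SAP 1.3: risk 30% under standard of care and a 25% relative reduction, hence 22.5% under CCP and a difference of 0.075, with 800 and 400 patients.

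**Step 1: reproduce the SAP 4.8 figure.** 2(1 − Φ(1.96/√0.5)) = 2(1 − Φ(2.772)) = 0.00557. This agrees with the printed 0.005573. At a first look, the error spent equals the nominal p-value threshold, so the figure is valid in itself.

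**Step 2: overall error of the printed pairs.** The interim and final statistics Z1 and Z2 are bivariate normal with correlation √t = √0.5. Overall error = 1 − P(|Z1| < c1, |Z2| < c2), where each c is the two-sided critical value of its level. For the interim values, c1 = 2.782 (0.0054) or 2.772 (0.005573).

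| Interim | Final | Overall error, t = 0.5 |
|---|---|---|
| 0.0054 | 0.0492 | 0.05129 |
| 0.005573 | 0.0492 | 0.05138 |

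A simulation of 20 million draws gave 0.0513 and 0.0514.

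**Step 3: solve for levels that give 0.05.**

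- After 0.0054, the final level is 0.04787.
- After 0.005573, it is 0.04778.
- For a final level of 0.0492, the interim level must be 0.00258, less than half of either printed value.
- Classical O'Brien-Fleming with two equally spaced looks has C = 1.9774. The interim critical value is 1.9774 × √2 = 2.7965, and the levels are 0.00517 and 0.04799.
- Spending 0.025 per side with the same type of function gives 0.00305 and 0.0490.

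None of these boundaries gives 0.0054 with 0.0492. That pair reaches 0.0500 only if the look falls at about 70% information.

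**Step 4: effect of re-estimation.** With θ = 0.5, the SAP 4.10 multiplier is 2 + 0.5 + 1/0.5 = 4.5. With (1.96 + 0.8416)² = 7.849 and a difference of 0.075, n = 4.5 × 7.849/0.075² × p(1 − p). The planned pooled rate is (800 × 22.5% + 400 × 30%)/1200 = 25%, which gives n = 1177, so no increase. If the look stays at 600 patients:

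| Pooled rate | N | t | Error, 0.0054/0.0492 | Error, 0.005573/0.0492 | Final level needed after 0.005573 |
|---|---|---|---|---|---|
| 30% | 1319 | 0.455 | 0.0516 | 0.0517 | 0.0475 |
| 35% | 1429 | 0.420 | 0.0518 | 0.0519 | 0.0472 |
| 50% | 1570 | 0.382 | 0.0521 | 0.0522 | 0.0470 |

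The last row is the ceiling of the formula, because p(1 − p) is largest at 50%.

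**Step 5: power.** For 30% against 22.5% with 400 and 800 patients and unpooled variance, power is 78.57% with 0.0054/0.0492, 78.22% with 0.005573/0.0478 and 78.25% with 0.0052/0.0480. Only the differences of 0.3 to 0.4 points bear on this concern. The planned 80% reproduces for a single test at 0.05 (80.1%), so the distance from 80% is not a cost of the correction.

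**The case against.** The strongest reply is that the rule is advisory. Protocol 4.9 calls it a guideline, Protocol 12.2.2 and SAP 4.8 call it a guide, and the IDSMC only recommends. If the efficacy boundary never stopped the trial, the error would be the final level itself, 0.0492, below 0.05. The 0.0513 arises if the boundary is always followed. The conditional-power guide for futility would, if always followed, bring the two-sided error down to about 0.028. This shows that the realised error depends on conduct. It does not rescue the printed numbers: SAP 4.7 presents them as the levels for formal and final significance, and a non-binding futility guide conventionally earns no credit against the type I error.

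A second reply is that SAP 4.8 covers only extra looks, as its opening suggests. That fails because the section goes on to compute the threshold for the planned 50% look, and Protocol 12.2.2 assigns the method to that look.

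A third reply is about scale, and it largely stands. The excess is 0.0013 to 0.0014. An exact enumeration of the unpooled Wald test at a single nominal 0.05 (400 and 800 patients, common event rate 20% to 35%) already gives a true size of about 0.0506 to 0.0509, so the large-sample approximation adds more than half as much again. The re-estimation figures add little, and the highest needs a pooled rate twice the planned one.

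Finally, the plan refers to a separate IDSMC guidance document, which may state one operative boundary. That limits any claim about what was applied, but it does not correct the SAP.

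**Conclusion.** The concern holds. The SAP gives two thresholds for one look, and its final level matches neither. If the boundary is followed at 50% information, the overall two-sided error is 0.0513 or 0.0514 against the stated 0.05. If the sample size rises after the look, it is at most 0.0521 with 0.0054, or 0.0522 with 0.005573.

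The practical effect is small. Under the null, the chance that the final p-value falls between about 0.0478 and 0.0492 is about 0.0014. The chance that the interim p-value falls between the two printed thresholds is about 0.0002. The point should be fixed because it concerns the decision level of the primary test, not because it is likely to change the result.

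The figures assume jointly normal test statistics, information proportional to the number of patients, and no credit for futility stopping.

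**What to change.** Choose one boundary and print its matched pair for a look at 50% information:

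- the SAP 4.8 spending function: interim 0.005573, final 0.0478. This is the natural choice, since Protocol 12.2.2 already assigns that method to the planned look; or
- classical O'Brien-Fleming, the rule named in SAP 4.7: interim 0.0052, final 0.0480.

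Other matched pairs are valid, such as 0.0031 with 0.0490 when 0.025 is spent per side, but that form appears nowhere in the documents. Delete the other interim value and 0.0492.

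Add one sentence: if the look does not fall at exactly 50%, or the sample size is changed under SAP 4.10, the final level is recomputed from the actual information fraction. A confidence interval at the matching level, beside the 95% interval, is optional.

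The cost is two numbers and one sentence in the SAP, no extra patients, and about 0.3 to 0.4 percentage points of power.
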